- 12. The patient has a current diagnosis of movement disorders that could mimic MSA; for example, Parkinson's disease, dementia with Lewy bodies, essential tremor, progressive supranuclear palsy, spinocerebellar ataxia, spastic paraparesis, corticobasal degeneration, or vascular, pharmacological or post-encephalitic parkinsonism, per investigator discretion. Patients who have previously been incorrectly diagnosed with Parkinson's disease will not be excluded
- 13. The patient has a history of moderate or severe head trauma or other neurological disorder or systemic medical disease that is, in the investigator's opinion, likely to affect CNS functioning
- 14. The patient has a history of neurosurgical procedures including deep brain stimulation that could, in the investigator's opinion, interfere with the assessments of safety or efficacy
- 15. The patient has contraindications for MRI
- 16. The patient has attempted suicide within the last 6 months or is at significant risk of suicide (either in the opinion of the investigator or defined as a "yes" to suicidal ideation questions 4 or 5 or answering "yes" to suicidal behaviour on the Columbia-Suicide Severity Rating Scale [C-SSRS] within the past 6 months)
- 17. The patient has a history of cancer, other than basal cell, Stage 1 squamous cell carcinoma of the skin or cured gastric or cervical carcinoma in situ, that has not been in remission for >5 years prior to the first dose of IMP
- 18. The patient takes or has taken recent or concomitant medication that is disallowed or allowed with restrictions (specified in Appendix II) or it is anticipated that the patient will require treatment with at least one of these medications during the study:
  - -Disallowed: any investigational products within 30 days before the Screening Visit, treatment targeting α-synuclein and/or MSA disease progression
  - -Allowed with restriction: stable dose for at least 8 weeks prior to randomization of drugs acting against parkinsonism (for example, Levodopa, Dopamine-Agonists, Amantadine and Monoamine oxidase B [MAO-B]-inhibitors) and/or drugs acting against autonomic

- dysfunction (for example, ephedrine, droxidopa, midodrine, fludrocortisone, octreotide, desmopressin, oxybutynin) and anticipated stable during the DBP. If medically necessary, initiation of or change of dose of concomitant medication is allowed per investigator discretion.

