# Appendix II Recent and Concomitant Medication Disallowed or Allowed with Restrictions

## **Recent and Concomitant Medication: Disallowed or Allowed with Restrictions**

In the table below, recent and concomitant medications that are disallowed or allowed with restrictions with respect to their use prior to or during the study are listed.

Drug Class	Details
Disallowed:	
Any investigational products	Disallowed within 30 days before the Screening Visit or 5 half-lives – whichever is longer, and throughout the whole study
Inhibitor of α-synuclein aggregation	Treatment targeting $\alpha$ -synuclein and/or MSA disease progression within the last 12 months and throughout the whole study
Monoclonal antibodies	anti-α-synuclein monoclonal antibody within the last 12 months and throughout the whole study
Vaccines	past or current treatment with an active vaccine targeting $\alpha$ -synuclein and throughout the whole study
Allowed with restriction:	Drugs acting against parkinsonism or autonomic dysfunction
Anticholinergic agents	All, stable dose for at least 8 weeks prior to randomization
Anticholinesterases	All, stable dose for at least 8 weeks prior to randomization
Cardiac stimulants	Adrenergic and dopaminergic agents, stable dose for at least 8 weeks prior to randomization
Corticosteroids for systemic use	Fludrocortisone; stable dose for at least 8 weeks prior to randomization
Dopaminergic agents	All, stable dose for at least 8 weeks prior to randomization
Drugs for urinary frequency and incontinence	All, stable dose for at least 8 weeks prior to randomization
Hypothalamic hormones	Octreotide; stable dose for at least 8 weeks prior to randomization
Posterior pituitary lobe hormones	Vasopressin and analogues; stable dose for at least 8 weeks prior to randomization
	randomization

If medically necessary, initiation of or change of dose of concomitant medication allowed with restriction is allowed per investigator discretion.

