7.2 Withdrawals

The number of patients who withdrew from the study will be summarized by primary reason for withdrawal and all reasons for withdrawal by period.

If relevant, Kaplan-Meier failure plots of time to withdrawal will be presented by treatment group for the DB-Period. The time will be calculated from the date of first dose of IMP to the date of withdrawal in the DB-Period. Patients who completed the DB-Period according to their individual treatment duration (48-72 weeks) will be regarded as censored at the End of treatment visit.

Patients who withdrew from the study will be listed and the listing will include the number of days in the study until withdrawal, the number of days on IMP, the primary reason for withdrawal, and all reasons for withdrawal.

All tables, graphs, and listings will be based on the FAS.

8 Demographics and Baseline Characteristics

Demographics (sex, age, race, region), Screening MRI findings supporting MSA diagnosis and CCI ; baseline disease characteristics (incl. MSA sub-type, CSF/blood NfL level, result from the qualitative alpha-synuclein seeding assay (SAA), time since symptom onset and diagnosis); baseline physical examinations and baseline efficacy variables will be summarized by treatment group and overall. Concurrent as well as relevant past medical and psychiatric disorders will be coded using the *Medical Dictionary for Regulatory Activities* (MedDRA) and summarized.

A concurrent medical or psychiatric disorder is a disorder that is ongoing at the baseline Visit. A past medical or psychiatric disorder is a disorder that ended prior to the baseline Visit.

Demographics and baseline characteristics will be summarized based on the APTS, PKS and SBS, and baseline efficacy variables will be summarized based on the FAS.

9 Recent and Concomitant Medication

Recent and concomitant medication will be coded using the *WHO Drug Dictionary* (WHO-DDE).

Medications will be classified according to the start and stop time and summarized by anatomical therapeutic chemical (ATC) code, and generic drug name:

- medication discontinued prior to first dose of IMP
- concomitant medication continued after first dose of IMP
- concomitant medication started at or after first dose of IMP

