In addition, concomitant medications continued or started after first dose of IMP will classified into two overall groups depending on purpose, i.e., treatment of motor symptoms ('anti-Parkinson medication') and treatment of autonomic dysfunction ('Autonomic dysfunction medication'). The classification will be done prior to unblinding according to Protocol Appendix VII.

The tables will be based on the APTS.

10 Exposure

For each infusion visit, information related to infusion completed as planned (yes/no), infusion temporarily interrupted (yes/no), and infusion lasted longer than 30 (+10) minutes (yes/no), as well as descriptive statistics for the duration of infusions (this duration includes duration of any infusion interruptions) and duration of temporary interruptions will be summarized by treatment group for the DB-Period and the OLE-Period, respectively.

Patients, who at any point during the study received a different dose than what was planned, will be listed for each period. The listing will include date of infusion visit, planned dose for the patient and actual dose received for the patient.

Exposure (days) to IMP will be calculated as:

(Date of last dose + 28 days) – Date of first dose + 1

Exposure to IMP will be summarized in weeks using descriptive statistics.

Study 18331A - Statistical Analysis Plan

Patient years of exposure (PYE) will be calculated as the sum of the number of days of exposure to IMP for each patient, divided by 365.25 days.

The number and percentage of patients with different durations of exposure (≤ 4 weeks, >4 to ≤ 8 weeks, >8 to ≤ 12 weeks, ..., >68 to ≤ 72 weeks) will be presented.

Exposure will be summarized based on the APTS. In addition, all infusion data will be listed.

11 Fall Diary Compliance

The Fall Diary is planned to be dispensed and filled out in 5 periods during the study, i.e., at a two-week Baseline period and at four post-baseline four-week periods, respectively. For each period, days where the fall diary has been missed will be summarized and presented by period and treatment group. Furthermore, the number of patients missing 7 days or more (at Baseline and at subsequent periods) and 14 days or more (at subsequent periods) in each period will be presented by period and treatment group.

A day where the fall diary has been missed is defined as a day where the subject did not fill out anything in the diary.

The summaries will be based on the FAS.

12 Wearable Compliance

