14.3.6 Subgroup Analyses of the Primary Endpoint

Subgroup analyses of the primary endpoint will be performed using the Bayesian repeated measures primary analysis model for the following subgroups:

- Use of concomitant medication (categorised into PD and autonomic dysfunction medication according to chapter 9). Two analyse will be performed: 1) where concomitant medication was already started up prior to baseline and continued after baseline, and 2) where concomitant medication was initiated or change in dose of existing medication after baseline
- Presence of MRI abnormalities at Screening supporting the diagnosis of MSA (i.e., 'yes' to at least one of the MRI abnormalities according to Screening MRI procedure)
- MSA sub-group (MSA-P and MSA-C)
- Pre-dose MSA positive result in the qualitative alpha-synuclein seeding aggregation assay (SAA), i.e., positive for alphaSyn seed amplification pattern predominantly found in subjects with MSA

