Appendix VII

Definition of Concomitant Medication Category

Name	ATC code	Category
etanautine	N04AB01	anti-parkinson medication
orphenadrine (chloride)	N04AB02	anti-parkinson medication
trihexyphenidyl	N04AA01	anti-parkinson medication
biperiden	N04AA02	anti-parkinson medication
biperiden	N04AA02	anti-parkinson medication
metixene	N04AA03	anti-parkinson medication
procyclidine	N04AA04	anti-parkinson medication
procyclidine	N04AA04	anti-parkinson medication
profenamine	N04AA05	anti-parkinson medication
dexetimide	N04AA08	anti-parkinson medication
dexetimide	N04AA08	anti-parkinson medication
phenglutarimide	N04AA09	anti-parkinson medication
mazaticol	N04AA10	anti-parkinson medication
bornaprine	N04AA11	anti-parkinson medication
tropatepine	N04AA12	anti-parkinson medication
benzatropine	N04AC01	anti-parkinson medication
etybenzatropine	N04AC02	anti-parkinson medication
neostigmine	N07AA01	Autonomic dysfunction medication
neostigmine	N07AA01	Autonomic dysfunction medication
pyridostigmine	N07AA02	Autonomic dysfunction medication
pyridostigmine	N07AA02	Autonomic dysfunction medication
distigmine	N07AA03	Autonomic dysfunction medication
distigmine	N07AA03	Autonomic dysfunction medication
ambenonium	N07AA30	Autonomic dysfunction medication
neostigmine, combinations	N07AA51	Autonomic dysfunction medication
tolcapone	N04BX01	anti-parkinson medication
entacapone	N04BX02	anti-parkinson medication
budipine	N04BX03	anti-parkinson medication
opicapone	N04BX04	anti-parkinson medication
levodopa	N04BA01	anti-parkinson medication
levodopa and decarboxylase inhibitor	N04BA02	anti-parkinson medication
levodopa, decarboxylase inhibitor and COMT inhibitor	N04BA03	anti-parkinson medication
melevodopa	N04BA04	anti-parkinson medication
melevodopa and decarboxylase inhibitor	N04BA05	anti-parkinson medication
etilevodopa and decarboxylase inhibitor	N04BA06	anti-parkinson medication
fludrocortisone	H02AA02	Autonomic dysfunction medication
etilefrine	C01CA01	Autonomic dysfunction medication
etilefrine	C01CA01	Autonomic dysfunction medication

Definition of Concomitant Medication Category

Name	ATC code	Category
isoprenaline	C01CA02	Autonomic dysfunction medication
isoprenaline	C01CA02	Autonomic dysfunction medication
norepinephrine	C01CA03	Autonomic dysfunction medication
dopamine	C01CA04	Autonomic dysfunction medication
norfenefrine	C01CA05	Autonomic dysfunction medication
phenylephrine	C01CA06	Autonomic dysfunction medication
dobutamine	C01CA07	Autonomic dysfunction medication

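### SAP Appendix VII leaves out dopamine agonists, amantadine and MAO-B inhibitors, so the anti-Parkinson medication subgroups of the primary endpoint can be misclassified

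*SAP*

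**What the plan says.** SAP chapter 9 has concomitant medications that were continued or started after first dose "classified into two overall groups depending on purpose, i.e., treatment of motor symptoms" on the one hand and autonomic dysfunction on the other. It then says how the sorting is done: "The classification will be done prior to unblinding according to Protocol Appendix VII".

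SAP Appendix VII is a table of drug name, ATC code and category. Its levodopa block ends at "etilevodopa and decarboxylase inhibitor" and the next row is fludrocortisone, in the autonomic category.

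Protocol 6.3, exclusion criterion 18, restricts "drugs acting against parkinsonism (for example, Levodopa, Dopamine-Agonists, Amantadine and Monoamine oxidase B [MAO-B]-inhibitors", and the synopsis gives the same four examples. Protocol Appendix II carries the restricted classes under the heading "Drugs acting against parkinsonism or autonomic dysfunction" and includes all dopaminergic agents without exception.

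The classification feeds the primary-endpoint subgroups in SAP 14.3.6: "Use of concomitant medication (categorised into PD and autonomic dysfunction medication according to chapter 9". Two analyses follow. The first concerns medication started before baseline and continued after it. The second is "where concomitant medication was initiated or change in dose of existing medication after baseline".

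**The concern.** The SAP describes the anti-Parkinson group by purpose but operates it through a closed list, and the list is narrower than the purpose. A dopamine agonist, amantadine or a MAO-B inhibitor given for motor symptoms fits the description and has no row. The appendix has no catch-all entry, and the SAP does not say what happens to an unlisted drug.

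At stake is who counts as treated for parkinsonism in two subgroup analyses of UMSARS TS. Part II of that score is a 14-item motor examination, so motor treatment is a natural thing to examine. The protocol also planned to examine Parkinson's medication as levodopa equivalent daily dose, both as a covariate (17.9.6) and as a subgroup (17.9.8). SAP 14.3.6 and 14.3.7 contain no such analysis, so more rests on the Appendix VII category.

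**Working it through.** The documents give no figure to reproduce here. The check is a count of the list, set against the protocol's own scope.

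**Count of anti-Parkinson rows in SAP Appendix VII**

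| ATC group | Rows | Distinct codes |
|---|---|---|
| N04AA | 13 | 10 |
| N04AB | 2 | 2 |
| N04AC | 2 | 2 |
| N04BA01–06 (levodopa products) | 6 | 6 |
| N04BX01–04 | 4 | 4 |
| Total | 27 | 24 |

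The difference of 3 arises because biperiden, procyclidine and dexetimide each appear twice.

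**Search for the classes the protocol names**

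- Levodopa: present.
- Dopamine agonists: 0 rows. Names searched: pramipexole, ropinirole, rotigotine, apomorphine, bromocriptine, cabergoline, pergolide.
- Amantadine: 0 rows.
- MAO-B inhibitors: 0 rows. Names searched: selegiline, rasagiline, safinamide.

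One of four named classes is listed and three are missing. They are not filed under the autonomic category either. The dopamine, ibopamine and fenoldopam rows there are coded C01CA and are not antiparkinsonian dopamine agonists.

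**Comparison with Protocol Appendix II.** That table has eight restricted classes: anticholinergics, anticholinesterases, cardiac stimulants, fludrocortisone, dopaminergic agents, urinary drugs, octreotide and vasopressin analogues. SAP Appendix VII has entries for all eight. It therefore reads as an implementation of that table with the dopaminergic part incomplete. SAP chapter 23, which records changes from the protocol, does not declare a narrower drug list.

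**Consequence if the list is followed**

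- First analysis (continued from before baseline): a patient whose only motor drug is in an omitted class becomes a non-user of anti-Parkinson medication. A patient who also takes levodopa is still classified correctly.
- Second analysis (started or dose changed after baseline): starting or changing an omitted drug is not counted, whether or not the patient takes levodopa. The protocol allows such changes at the investigator's discretion, so they can occur.
- The two-group medication summary in SAP chapter 9 has the same gap.

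**Possible size, by assumption only.** If a share p of the 60 randomised patients takes only an omitted class, 60 × p are misfiled in the first analysis:

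- p = 2%: 60 × 0.02 = 1.2
- p = 5%: 60 × 0.05 = 3
- p = 10%: 60 × 0.10 = 6
- p = 20%: 60 × 0.20 = 12

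**The case against.** The strongest reply is that this is a short list in a minor place. The protocol's four classes are introduced as examples and serve stable-dose eligibility rules, not analysis. Every drug is still coded and "summarized by anatomical therapeutic chemical (ATC) code, and generic drug name", so an uncategorised drug would be visible, and the sorting takes place before unblinding. Protocol 2.1.1 does not regard dopamine agonists as a therapeutic option, so use of that class may be low. SAP 14.3.6 also does not spell out its user and non-user levels: if any listed drug of either kind made a patient a user, some patients would not move.

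Part of this stands. The reach is limited and the likely effect for dopamine agonists may be small, although the remark in 2.1.1 does not cover amantadine or MAO-B inhibitors. Visibility in the ATC tables makes an unnoticed error less likely, but those tables do not define the subgroups. The pooled reading does not fit SAP 14.3.6, which splits medication into PD and autonomic categories.

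It can also be said that the list plainly governs over purpose. That removes the ambiguity but makes the omission firmer, because the drugs are then excluded by rule.

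Two cautions remain. Amantadine can be checked by name from the document alone, while the absence of the other two classes relies on general knowledge of which drugs belong to them. Loss of rows in text extraction is unlikely, since the rows run without a visible break into fludrocortisone, but a look at the source PDF would settle it.

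**Conclusion.** The concern holds. SAP Appendix VII omits three of the four antiparkinsonian classes the protocol names, with 0 of 27 rows between them. Followed as written, it would misfile sole users of those classes and miss starts and dose changes of those drugs.

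The reach is one of the four subgroup items in SAP 14.3.6 (two analyses) and the two-group summary in SAP chapter 9. These are supportive and outside the testing strategy; the primary analysis, type I error and power are unaffected. The number of patients concerned cannot be derived from the documents, and the range of about 1 to 12 of 60 rests wholly on the assumed 2% to 20%. The change should be made before unblinding, because a later repair would be made with treatment known.

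**What to change.** Before unblinding, complete SAP Appendix VII so that its anti-Parkinson category covers every antiparkinsonian class the protocol names. That means adding dopamine agonists, amantadine and MAO-B inhibitors, with codes taken from the drug dictionary in use. If any class is left out on purpose, give the reason.

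Add a sentence to SAP chapter 9 saying whether purpose or the list decides for a drug that is not listed. As a clerical point, change the reference there from Protocol Appendix VII to SAP Appendix VII.

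The cost is a few appendix rows, one sentence and one corrected reference. No new data are needed, and the change concerns the coding of recorded medication only.

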14.1 Overview of Planned Efficacy Analyses in the DB-Period

An overview of all planned efficacy analyses is provided in Panel 2. Where relevant, the analyses will be presented by visit. Endpoints related to as 'disease progression' (primary and selected secondary endpoints) will be analysed using a 'Bayesian' progression model; remaining continuous variables will be analysed applying a MMRM in a Frequentist framework, where stated.

Variables	Туре	Priority	Description
UMSARS TS	1	1	Sum of UMSARS Part I+II items (Primary)
mUMSARS score	1	2	Sum of Part I items with respond option 0 and 1 collapsed
UMSARS Part I score	1	3	Sum of UMSARS Part I items
UMSARS part II score	1	3	Sum of UMSARS Part II items
aUMSARS score	1	4	Sum of UMSARS Part I+II selected items - PI: 1,3,4,7,8 & PII: 2,6,8,11,14
SE-ADL score	2	3	Schwab and England Activities of Daily Living scale: sum of items
CGI-S score	2	3	Global impression severity, Clinical: sum of items
PGI-S score	2	3	Global impression severity, Patient: sum of items
OGI-S score	2	3	Global impression severity, Observer-reported: sum of items
COMPASS select change	2	3	Composite autonomic symptom: a score for each domain
UMSARS part III items	2	4	Heart rate, sys/dia blood pressure; individual items
UMSARS part III items	3	4	orthostatic symptoms; individual item
UMSARS part IV item	3	3	Global disability: UMSARS single item
UMSARS part I items	3	3	Disease milestones: Speech, swallowing, walking and falls; UMSARS Part I single items
Patient fall diary	3	3	Disease milestones: Frequency, cause and consequence of falls; patient dairy derived
Use of wheelchair	4	4	Disease milestones: Wheelchair – time to full time user; according to physical examination
PamSys digital device	3	4	Disease milestones: Frequency of Falls; PamSys derived
FeetMe digital device	2	4	Disease milestones: gait parameters; FeetMe derived
EQ-5D-5L items	3	3	Health-related quality of life: domain scores
EQ-5D-5L VAS score	2	3	Health-related quality of life: VAS score
MRI, volumetric (vMRI)	2	3	volume in ROIs (e.g., caudate nucleus, putamen, striatum, pons, brain stem, grey matter and cerebellum)

Panel 2 Overview of Planned Efficacy Analyses (DB-Period)

Study 18331A – Statistical Analysis Plan

Variables	Туре	Priority	Description
MRI, diffusivity (DTI MRI)	2	4	Mean diffusivity in ROIs (e.g., caudate nucleus, putamen, globus pallidus, pons, cerebellar cortex and white matter and middle cerebellar peduncle, both FA and MD)
Blood biomarkers	2	3, 4	neurofilament light (NfL) concentrations [2], 'free' and 'total' α -synuclein [3]
CSF biomarkers	2	4	concentrations of t-tau, NfL, 'free' and 'total' α -synuclein, pathological species of α -synuclein
MRI, arterial spin (ASL)	2	4	Mean Cerebral blood flow in ROIs (e.g., putamen and cerebellum)
Type: 1 = continuous_Bayes; 2 = continuous_Other; 3 = categorical; 4 = time to event; Priority: 1 = Primary; 2 = Key Secondary; 3 = Secondary; 4 = Exploratory			

14.2 General Efficacy Analysis Methodology

Unless otherwise specified, all efficacy analyses will be based on the FAS for the observed case (OC) data.

For endpoints analysed in the Bayesian framework, the success threshold for the Bayesian posterior probability of superiority relative to placebo [Prob(θ <1)] has been calibrated using simulations to correspond to a significance level of 5% applied one-sided. By doing so a success threshold of 0.975 has been identified which will be used to evaluate the primary endpoint and remaining endpoints evaluated by the Bayesian progression model. A burn-in of 1000 samples will be used for the Bayesian analysis.

All statistical tests of the secondary efficacy endpoints will be presented two-sided on a 5% significance level.

A testing strategy will be applied including the primary analysis on UMSARS TS and the key secondary analysis on mUMSARS to protect the type I error on an overall one-sided 5% significance level for these analyses. Further details to be found in chapter 15.

For analysis of exploratory efficacy data collected in the open-label extension, the original placebo patients will be presented as a separate group and hence there will be no pooling of treatment groups.

